3.2.3 Interruption or discontinuation of treatment

For patients who are unable to tolerate the protocol-specified dosing schedule, dose adjustments are permitted in order to keep the patient on study drug. If administration of RAD001 must be interrupted because of unacceptable toxicity, drug dosing will be interrupted or modified according to rules described in Table 3-1. Toxicity will be assessed using the NIH-NCI Common Terminology Criteria for Adverse Events, version 3.0 (CTCAEv3.0, (<http://ctep.cancer.gov/forms/CTCAEv3.pdf>)).

Table 3.0 RAD001 dose level modification guidelines

Dose level	Dose and schedule
0 (starting dose)	10 mg daily
-1	5 mg daily
-2	5 mg every other day

Table 3-1 Criteria for dose-modification in case of suspected RAD001 toxicity and re-initiation of RAD001 treatment

Toxicity	Actions
Non-hematological toxicity	
Grade 2 (except pneumonitis – refer to Table 3-2)	If the toxicity is tolerable to the patient, maintain the same dose. If the toxicity is intolerable to patient, interrupt RAD001 until recovery to grade ≤ 1 . Then reintroduce RAD001 at same dose. If event returns to grade 2, then interrupt RAD001 until recovery to grade ≤ 1 . Then reintroduce RAD001 at the lower dose level.
Grade 3 (except hyperlipidemia*) (except pneumonitis – refer to Table 3-2)	Interrupt RAD001 until recovery to grade ≤ 1 . Then reintroduce RAD001 at the lower dose level. For pneumonitis consider the use of a short course of corticosteroids.
Grade 4	Discontinue RAD001.
Hematological toxicity	
Grade 2 Thrombocytopenia (platelets $<75, \geq 50 \times 10^9/L$)	Interrupt RAD001 until recovery to grade ≤ 1 ($>75 \times 10^9/L$). Then reintroduce RAD001 at initial dose. If thrombocytopenia again returns to grade 2, interrupt RAD001 until recovery to grade ≤ 1 . Then reintroduce RAD001 at the lower dose level.
Grade 3 Thrombocytopenia (platelets $<50, \geq 25 \times 10^9/L$)	Interrupt RAD001 until recovery to grade ≤ 1 (platelets $\geq 75 \times 10^9/L$). Then resume RAD001 at one dose level lower. If grade 3 thrombocytopenia recurs, discontinue RAD001.
Grade 4 Thrombocytopenia (platelets $< 25 \times 10^9/L$)	Discontinue RAD001.
Grade 3 Neutropenia (neutrophils $<1, \geq 0.5 \times 10^9/L$)	Interrupt RAD001 until recovery to grade ≤ 1 (neutrophils $\geq 1.5 \times 10^9/L$). Then resume RAD001 at the initial dose. If ANC again returns to Grade 3, hold RAD001 until the ANC $\geq 1.5 \times 10^9/L$. Then resume RAD001 dosing at the lower dose level. Discontinue patient from study therapy for a third episode of grade 3 neutropenia.
Grade 4 Neutropenia (neutrophils $< 0.5 \times 10^9/L$)	Interrupt RAD001 until recovery to grade ≤ 1 (neutrophils $\geq 1.5 \times 10^9/L$). Then resume RAD001 at the lower dose level. If grade 3 or grade 4 neutropenia occurs despite this dose reduction, discontinue RAD001.
Grade 3 febrile neutropenia (not life-threatening)	Interrupt RAD001 until resolution of fever and neutropenia to grade ≤ 1 . Hold further RAD001 until the ANC $\geq 1,500/\text{mm}^3$ and fever has resolved. Then resume RAD001 at the lower dose level. If febrile neutropenia recurs, discontinue RAD001.
Grade 4 febrile neutropenia (life-threatening)	Discontinue RAD001.
Any hematological or non-hematological toxicity requiring interruption for ≥ 28 days.	Discontinue RAD001

*Grade 3 hyperlipidemia (hypercholesterolemia and/or hypertriglyceridemia) should be managed using medical therapies (see Sec. 3.2.5.2).

3.2.4 Monitoring of RAD001 suspected toxicities

Patients whose treatment is interrupted or permanently discontinued due to an adverse event or abnormal laboratory value suspected to be related to RAD001 must be followed at least weekly until the adverse event or abnormal laboratory resolves or returns to grade 1. If a patient requires a dose delay of > 28 days from the intended day of the next scheduled dose, then the patient must be discontinued from the study.

3.2.5 Known Undesirable Side Effects of RAD001

The data described below reflect exposure to everolimus (n=274) and placebo (n=137) in a randomized phase III study for the treatment of metastatic renal cell carcinoma. In total, 165 patients were exposed to everolimus 10 mg/day for \geq 4 months. The median age of patients was 61 years (range 27 to 85). The most common adverse reactions (incidence \geq 10%) were stomatitis, rash, fatigue, asthenia, diarrhea, anorexia, nausea, mucosal inflammation, vomiting, cough, peripheral edema, infections, dry skin, epistaxis, pruritus, and dyspnoea. The most common grade 3-4 adverse reactions (incidence \geq 2%) were infections, stomatitis, fatigue, and pneumonitis.

The median duration of blinded study treatment was 141 days (range 19 to 451) for patients receiving everolimus and 60 days (range 21 to 295) for those receiving placebo. The rates of treatment-emergent adverse reactions resulting in permanent discontinuation were 7% and 0% for the everolimus and placebo treatment groups, respectively. Most treatment-emergent adverse reactions were grade 1 or 2 in severity. Grade 3 or 4 treatment-emergent adverse reactions were reported in 39% versus 7% of patients receiving everolimus and placebo, respectively. Deaths due to acute respiratory failure (0.7%), infection (0.7%), and acute renal failure (0.4%) were observed on the everolimus arm.

Everolimus has immunosuppressive properties and may predispose patients to bacterial, fungal, viral or protozoan infections, including infections with opportunistic pathogens. Localized and systemic infections, including pneumonia, other bacterial infections, invasive fungal infections, such as aspergillosis or candidiasis and viral infections including reactivation of hepatitis B virus, have been described in patients taking everolimus. Some of these infections have been severe (e.g. leading to respiratory or hepatic failure) and occasionally have had a fatal outcome.

Physicians and patients should be aware of the increased risk of infection with everolimus. Treat pre-existing infections prior to starting treatment with everolimus. While taking everolimus, be vigilant for symptoms and signs of infection; if a diagnosis of infection is made, institute appropriate treatment promptly and consider interruption or discontinuation of everolimus. If a diagnosis of invasive systemic fungal infection is made, discontinue everolimus and treat with appropriate antifungal therapy.

Reactivation/flare of Hepatitis B (HBV) has been observed in patients with cancer receiving chemotherapy (Yeo 2004). Sporadic cases of Hepatitis B reactivation have also been seen in
Protocol: RAD001

Version 7.0 03/15/2011

this setting with everolimus. Use of antivirals during anti-cancer therapy has been shown to reduce the risk of Hepatitis B virus reactivation and associated morbidity and mortality (Loomba 2008). A detailed assessment of Hepatitis B/C medical history must be done for all patients at screening, with testing performed prior to the first dose of everolimus.

Hypersensitivity reactions manifested by symptoms including, but not limited to, anaphylaxis, dyspnea, flushing, chest pain or angioedema (e.g. swelling of the airways or tongue, with or without respiratory impairment) have been observed with everolimus.

Hyperglycemia has been reported in clinical trials. Monitoring of fasting serum glucose is recommended prior to the start of everolimus therapy and periodically thereafter. Optimal glycemic control should be achieved before starting a patient on everolimus. Mouth ulcers, stomatitis and oral mucositis have been seen in patients treated with everolimus. In such cases topical treatments are recommended, but alcohol- or peroxide-containing are not allowed.

Elevations of serum creatinine, usually mild, have been reported in clinical trials. Monitoring of renal function, including measurement of blood urea nitrogen (BUN) or serum creatinine, is recommended prior to the start of everolimus therapy and periodically thereafter.

Decreased hemoglobin, lymphocytes, platelets and neutrophils have been reported in clinical trials. Monitoring of complete blood count is recommended prior to the start of everolimus therapy and periodically thereafter.

Everolimus is not recommended in patients with severe hepatic impairment, (Child-Pugh class C).

The use of live vaccines and close contact with those who have received live vaccines should be avoided during treatment with everolimus.

Hypophosphatemia, hypomagnesemia, hyponatremia and hypocalcemia have been reported as serious adverse reactions. Electrolytes should be monitored in patients treated with RAD001.

Table 3-1 provides general recommendations for the management of patients, with suspected drug toxicities while on treatment with RAD001 as single-agent therapy.

More detailed information regarding RAD001 reported suspected toxicities and individual cases is provided in the [Investigator's Brochure].

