Agents containing hydrogen peroxide, iodine, and thyme derivatives may tend to worsen mouth ulcers. It is preferable to avoid these agents. Antifungal agents must be avoided unless a fungal infection is diagnosed. In particular, systemic imidazole antifungal agents (ketoconazole, fluconazole, itraconazole, etc.) should be avoided in all patients due to their strong inhibition of RAD001 metabolism, therefore leading to higher RAD001 exposures. Therefore, topical antifungal agents are preferred if an infection is diagnosed. Similarly, antiviral agents such as acyclovir should be avoided unless a viral infection is diagnosed.

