3.3.3 Concomitant therapy

All concomitant medications administered within 14 days of enrollment through treatment termination should be reported to the investigator and recorded in the Case Report Form (CRF). In particular, corticosteroid dosing will be recorded as use of corticosteroids may affect the appearance of T2 changes on MRI imaging. In addition, the definition of response is based on corticosteroid use (see section 3.42).

Patients will be instructed not to take any additional medications (including over-the-counter products) during the course of the study without prior consultation with the investigator. At each visit, the investigator will ask the patient about any new medications he/she is or has taken after the start of the study drug.

All Concomitant medications/Significant non-drug therapies taken \leq 30 days prior to start and after start of study drug, including physical therapy and blood transfusions, should be recorded.

The following restrictions apply during the entire duration of the study:

- No other investigational therapy should be given to patients.
- No anticancer agents other than the study medication should be given to patients. If such agents are required for a patient then the patient must first be withdrawn from the study.
- Oral contraceptives in preclinical and clinical data have shown everolimus to have CYP3A4 inhibitory activity rather than induction activity, induction of metabolism of contraceptive hormones by everolimus is unlikely. Consequently, administration of everolimus should not reduce the efficacy of oral contraceptives.

Inhibitors of CYP3A4 and/or PgP

- Co-administration with strong inhibitors of CYP3A4 (e.g., ketoconazole, itraconazole, ritonavir) or P-glycoprotein (PgP) should be avoided

- Seville orange, star fruit, grapefruit and their juices affect P450 and PgP activity. These juices are potent CYP3A4-inhibitors. Concomitant use should be avoided
- Co-administration with moderate CYP3A4 inhibitors (e.g., erythromycin, fluconazole) or PgP inhibitors should be used with caution. If patient requires co-administration of moderate CYP3A4 inhibitors or PgP inhibitors, reduce the dose of RAD001 to 2.5 mg daily. Additional dose reductions to every other day may be required to manage toxicities. If the inhibitor is discontinued the RAD001 dose should be returned to the dose used prior to initiation of the moderate CYP3A4/PgP inhibitor after a washout period of 2 to 3 days.

Inducers of CYP3A4 and/or PgP

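### Table 3-1 makes no exception for invasive systemic fungal infection, so its grade 3 row, read alone, restarts a drug that section 3.2.5 says to stop

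*Combined protocol and SAP*

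**What the plan says.** Section 3.2.5 describes everolimus as immunosuppressive and lists invasive fungal infections among the infections seen with it. For infections in general it asks the physician to consider either interrupting or discontinuing. For this one it leaves no choice: "If a diagnosis of invasive systemic fungal infection is made, discontinue everolimus and treat with appropriate antifungal therapy". No grade is named and no restart is described.

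Section 3.2.3 governs dosing after toxicity. When "administration of RAD001 must be interrupted because of unacceptable toxicity, drug dosing will be interrupted or modified according to rules described in Table 3-1", the reader is sent to that table. Its grade 3 non-hematological row is headed "Grade 3 (except hyperlipidemia*) (except pneumonitis", with the pneumonitis exception pointing to Table 3-2. The action is to interrupt until recovery to grade 1 or less, and then: "Then reintroduce RAD001 at the lower dose level. For pneumonitis consider the use of a short course of corticosteroids". The grade 2 row excepts only pneumonitis. The grade 4 row discontinues. The last row, "Any hematological or non-hematological toxicity requiring interruption for" 28 days or more, also discontinues. No row or footnote mentions fungal infection.

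Section 3.2.5 later describes the table in softer terms: "Table 3-1 provides general recommendations for the management of patients, with suspected drug toxicities while on treatment with RAD001 as single-agent therapy".

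**The concern.** A clinician deciding a dose is likely to go to the table, because section 3.2.3 says its rules will be followed. For a grade 3 invasive fungal infection that settles quickly, the table supplies a restart rule and no cue to look elsewhere. The instruction to stop is one sentence in a side-effects narrative several pages later.

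What is at stake is re-exposure to an immunosuppressant after an infection of a kind that section 3.2.5 treats as dangerous. That section says some of the listed infections were severe and occasionally fatal. The matter is one of patient safety, not inference.

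**Working it through.** The plan states no figure on this point and no calculation applies. The check sets the two instructions side by side.

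**Does the table cover these events?** Table 3-1 is for suspected RAD001 toxicity. Section 3.2.5 says everolimus may predispose to fungal infection and lists infections among the most common grade 3-4 reactions. A fungal infection that the investigator suspects is drug-related therefore falls in the non-hematological rows unless excepted.

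**Where do the instructions differ?**

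| Situation | Section 3.2.5 | Table 3-1 read alone | Agree? |
|---|---|---|---|
| Grade 2 | Stop | Continue if tolerable; otherwise hold, then resume | Differs only if such an event can be graded 2 |
| Grade 3, at grade 1 or less in under 28 days | Stop | Hold, then resume one level lower | No |
| Grade 3, interruption of 28 days or more | Stop | Stop | Yes |
| Grade 4 | Stop | Stop | Yes |

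The documents cite CTCAE version 3.0 but do not reproduce its infection criteria, so a grade 2 conflict is not claimed. The established conflict is the second row. By Table 3.0, one level below the 10 mg starting dose is 5 mg daily.

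**Could stopping in section 3.2.5 simply mean holding?** Probably not. The sentence before the fungal instruction offers interruption and discontinuation as alternatives, and the fungal sentence then names only the second. Table 3-1 also uses the two words for different actions. Against this, section 3.2.5.4 says everolimus should be discontinued for grade 3 pneumonitis and then allows it to be started again at a reduced dose. There the permission is express; for fungal infection none is given. Permanence is thus a reasonable inference, but it is not stated.

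**Does the table flag its other departures?** Yes. Pneumonitis is sent to Table 3-2, and grade 3 hyperlipidemia has a footnote to section 3.2.5.2. Fungal infection has neither a row nor a footnote.

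**Does it reach the analysis?** No. Section 6.1.2 counts progression and death whether or not the patient is still on drug, and analyzes by intention to treat.

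**The case against.** The strongest reply is that the protocol already resolves the matter. Section 3.2.5 is specific and unconditional, and the same section calls the table general. An investigator who reads the whole protocol stops the drug. The link in section 3.2.3 is also conditional: it applies when dosing must be interrupted, whereas section 3.2.5 calls for discontinuation, so the reintroduction step need never be reached. Nor is the table exhaustive. Hepatitis B reactivation is absent from it too, yet section 3.2.5.3 takes the patient off protocol. Finally, section 3.4.5 provides monthly discussion of each patient and committee review of serious adverse events.

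Much of this stands. It settles which text should control, and it rules out the stronger reading that a reader might infer, namely that the protocol orders a restart after invasive fungal infection. Taken as a whole, it does not.

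What survives is the table itself. Section 3.2.3 still calls its contents rules, and its grade 3 wording is broad enough to cover the event. The hepatitis B comparison is weaker than it looks: that event has its own subsection and appears in the list of discontinuation reasons after Table 3-2, and fungal infection has neither. Oversight review would not necessarily come before a restart.

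A reader might also be tempted to size the problem by the antifungal in use. Section 3.2.5.1 says that "systemic imidazole antifungal agents (ketoconazole, fluconazole, itraconazole, etc.) should be avoided in all patients due to their strong inhibition of RAD001 metabolism". Section 3.3.3 says to avoid strong inhibitors and, for moderate ones: "If patient requires co-administration of moderate CYP3A4 inhibitors or PgP inhibitors, reduce the dose of RAD001 to 2.5 mg daily". Combining these with Table 3-1 would give a range of restart doses, but that is a list of dose levels under a combination the documents never spell out. It measures neither risk nor frequency, and the interaction is already addressed in those sections. It should not be used as a measure of impact.

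**Conclusion.** The point holds as a narrow safety inconsistency in the dosing table. It is confined to a grade 3 invasive systemic fungal infection that recovers to grade 1 or less in under 28 days, handled by someone using Table 3-1 without section 3.2.5. The documents give neither a rate for this infection nor the share that would meet those conditions, so the number of patients cannot be estimated. It is probably very small.

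The conclusion assumes that the infection is treated as a suspected RAD001 toxicity and that discontinuation in section 3.2.5 means more than a temporary hold. A reader might go further and say that section 3.2.5 expressly bars any later restart. It does not say so, and the pneumonitis text shows that the word alone does not settle it. The correction is still worth making, because the table gives the wrong action for a potentially fatal event and the change is nearly free.

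**What to change.** In the grade 2 and grade 3 non-hematological rows of Table 3-1, add: *except invasive systemic fungal infection: discontinue RAD001, see section 3.2.5*. This follows the way pneumonitis is already handled. Including the grade 2 row closes the same gap without having to decide whether such an event can be graded 2.

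The sponsor should first confirm whether discontinuation is meant to be permanent. If so, *do not reintroduce* can be added; without that confirmation it would put a prohibition in the table that the protocol does not state.

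The cost is a wording change in two rows of one table. It needs no new procedures, visits or patients.

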3.2.5.2 Management of hyperlipidemia and hyperglycemia

Treatment of hyperlipidemia should take into account the pre-treatment status and dietary habits. Blood tests to monitor hyperlipidemia must be taken in the fasting state. Hyperlipidemia and hypertriglyceridemia should be treated according to local best clinical practice. Patients should be monitored clinically and through serum chemistry for the development of rhabdomyolysis and other adverse events as required in the product label/data sheets for HMG-CoA reductase inhibitors.

Hyperglycemia has been reported in clinical trials. Monitoring of fasting serum glucose is recommended prior to the start of everolimus therapy and periodically thereafter. Optimal glycemic control should be achieved before starting trial therapy.

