3.4 Visit schedule and assessments

3.4.1 Visit schedule

3.4.1.1 Screening Assessments

Written informed consent must be obtained and documented in the medical record before starting protocol therapy. After receiving a subject's agreement to participate in the study and verifying that the subject eligibility criteria, the study site will begin further pretreatment evaluation as follows:

- Clinical Evaluation: A complete history and neurological examination (including clinical assessment of Karnofsky Performance Status, Neurological function, neurologic exam score, Vital signs, Physical, and Mental Status) is to be done within 14 days of initial protocol treatment.
- Radiographic Evaluation: An MRI scan must be performed within 14 days prior to initial treatment on a dose of steroids that has been stable or decreasing for 5 days or more. MR spectroscopy are optional.
- Vital Signs: Height, pulse, blood pressure, respiration rate, temperature and weight. Blood pressure, pulse and respiration rate should be measured on patients.
- Laboratory Evaluation: Blood tests may be performed at the UCSF GCRC, at the UCSF Neuro-oncology clinic, or at a local laboratory. Pre-study laboratory tests must be obtained with 14 days prior to initial protocol treatment. Pre-study laboratory tests shall include:
 - CBC, platelets, differential, PT (INR)
 - Sodium, potassium, chloride, bicarbonate, calcium, fasting glucose, albumin, total protein, BUN, serum creatinine
 - T. bilirubin, AST, ALT, alkaline phosphatase, uric acid, phosphorus,
 - Fasting serum lipid profile (total cholesterol, triglycerides, HDL and LDL)
 - serum pregnancy test for women of childbearing potential (performed within 7 days of initial protocol treatment).

- Electrocardiogram (ECG): A standard 12 lead ECG is to be performed within 14 days of initial protocol treatment and significant findings must be recorded.
- Lung function: Pulse Oximetry and Chest X-ray must be performed within 14 days prior to initial protocol treatment

Hepatitis B/C testing: Patients will be tested for the following hepatitis serologic markers: HBsAg, HBs Ab, HBc Ab Total, HBc IgM Ab and HCV antibodies.

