3.4.1.2. Assessments During Treatment

- Clinical Evaluation: Clinical assessments will be required every 2 months for the first 12 months, then every 3 months for the next 12 months. After 4 weeks of treatment, a toxicity check will be performed with a local MD or telephone. Whenever possible, all assessments at each scheduled time-point will be completed in a single clinic visit. Performance of a full clinical evaluation should take between 1-1.5 hours. Clinical assessments performed at required visits will include the following:

Karnofsky performance status (Appendix 17.2)

Neurological function / Neurologic exam (see below)

Physical Examination

Pulse Oximetry measurements

Neuro Exam: Neurologic status should be recorded at each patient visit according to the scale below (compared to baseline, defined as neurologic exam at time of screening).

+2	Definitely better
+1	Possibly better
0	Unchanged
-1	Possibly worse
-2	Definitely worse

Vital Signs: pulse, blood pressure, respiration rate, temperature and weight. Blood pressure, pulse and respiration rate should be measured on patients

- Radiographic Evaluation: An MRI will be required every 2 months for 12 months and every 3 months for the next 12 months. MR spectroscopy scans at these time points are optional. A research MRI/MRS scan maybe performed during Cycle 1 week 3. Required assessments will include measurement of bi-

directional diameters for patients who continue to have measurable disease. Uni-dimensional maximal diameter will also be recorded. MRI will be evaluated by Central Radiology review by both a neuro-oncology attending.

- Chest X-ray: A chest x-ray is required every 2 months for 12 months and every 3 months for the next 12 months.

Course Response: This will be recorded every time a patient has an imaging study.

+3	=	Disappearance of tumor (CR)
+2	=	Definitely better (PR)
+1	=	Possibly better
0	=	Unchanged
-1	=	Possibly worse
-2	=	Definitely worse (PD)
-3	=	Development of a new lesion (PD)

- Laboratory Evaluation: Laboratory tests except serum pregnancy tests shall be performed every 2 weeks during the first 2 months of treatment, and then monthly thereafter:
 - CBC, platelets, differential
 - Sodium, potassium, chloride, bicarbonate, calcium, fasting glucose, albumin, total protein, BUN, serum creatinine
 - T. Bilirubin, AST, ALT, alkaline phosphatase, uric acid, phosphorus
 - Fasting serum lipid profile (total cholesterol, triglycerides, HDL and LDL)

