3.4.7.2 Laboratory evaluations

- *please see section 3.4.1 for schedule for initial assessment and during follow up*

Hematology

Hematology must include hemoglobin, hematocrit, platelets, total white blood cell count (WBC) and differential. PT (INR) evaluation will be included for baseline evaluations.

Blood chemistry

Blood chemistry must include sodium, potassium, chloride, bicarbonate, calcium, glucose, creatinine, blood urea nitrogen, albumin, total protein, SGOT (AST), SGPT (ALT), total bilirubin, alkaline phosphatase, uric acid, phosphorus, serum lipid profile (triglycerides, total cholesterol, HDL and LDL).

Because accurate serum glucose and lipid measurements are required, patients should be fasting at the time of the blood sampling.

Hepatitis B Virus testing

Patients will be tested for the following hepatitis B serologic markers prior to enrolling on the trial: HBsAg, HBs Ab, and HBc Ab Total, and HBc IgM Ab.

HbsAg monitoring should be performed every 4 weeks if a patient tests positive for the hepatitis B antibodies without prior vaccination

Hepatitis C Virus testing

Patients will be tested for HCV Ab prior to enrolling on the trial.

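### Hypomagnesemia is named as a serious adverse reaction and electrolytes are to be monitored, but no laboratory list schedules or requires serum magnesium

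*Combined protocol and SAP*

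**What the plan says.** Section 3.2.5, on the known side effects of RAD001, states: "Hypophosphatemia, hypomagnesemia, hyponatremia and hypocalcemia have been reported as serious adverse reactions. Electrolytes should be monitored in patients treated with RAD001". It does not say which electrolytes are meant, but the preceding sentence names the four disturbances that prompt the instruction.

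The tests themselves are set out in three places:

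- **Screening, section 3.4.1.1.** One line runs from sodium to serum creatinine. Another reads "T. bilirubin, AST, ALT, alkaline phosphatase, uric acid, phosphorus".
- **On treatment, section 3.4.1.2.** The lines are "Sodium, potassium, chloride, bicarbonate, calcium, fasting glucose, albumin, total protein, BUN, serum creatinine" and "T. Bilirubin, AST, ALT, alkaline phosphatase, uric acid, phosphorus". These tests are to be "performed every 2 weeks during the first 2 months of treatment, and then monthly thereafter".
- **Definition of blood chemistry, section 3.4.7.2.** "Blood chemistry must include sodium, potassium, chloride, bicarbonate, calcium, glucose, creatinine, blood urea nitrogen, albumin, total protein". Further on, the same list adds phosphorus, along with liver tests, uric acid and lipids.

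The summary table in section 3.4.1.4 has only a generic row for chemistries. Section 3.4.3 refers to blood chemistry without naming analytes.

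**The concern.** The protocol identifies a risk, asks for it to be watched, and then gives sites a test list that leaves it out. A site that follows the lists exactly meets the instruction for three of the four named disturbances and obtains no information on the fourth.

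Several safety mechanisms in the plan work best with, or depend on, a measured value:

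- Table 3-1 (section 3.2.3) sets its actions by toxicity grade.
- Section 3.2.4 requires at least weekly follow-up when a suspected drug-related laboratory abnormality leads to interruption or discontinuation.
- Section 3.4.6 compares grade 3 or 4 adverse event rates with the Investigator's Brochure or package insert. A disturbance that is not routinely tested for will tend to look reassuring in that comparison.
- The first secondary objective in section 2 is to describe further the safety of RAD001 in this population. Without baseline values, pre-existing low magnesium cannot be separated from low magnesium that emerges on treatment.

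The omission looks like an oversight. The other laboratory monitoring statements in section 3.2.5 (fasting glucose, renal function, complete blood count, hepatitis testing) all have matching tests in sections 3.4.1.1 and 3.4.1.2. No reason is given for treating magnesium differently.

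**Working it through.** The plan states no figure to reproduce. The check matches the four disturbances named in section 3.2.5 against the three itemised lists.

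| Named disturbance | Analyte | Screening (3.4.1.1) | On treatment (3.4.1.2) | Chemistry definition (3.4.7.2) | Lists covering it |
|---|---|---|---|---|---|
| Hypophosphatemia | Phosphorus | yes | yes | yes | 3 of 3 |
| Hyponatremia | Sodium | yes | yes | yes | 3 of 3 |
| Hypocalcemia | Calcium | yes | yes | yes | 3 of 3 |
| Hypomagnesemia | Magnesium | no | no | no | 0 of 3 |

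The two less specific places do not close the gap. The chemistries row in section 3.4.1.4 names no analytes, and neither does section 3.4.3. The laboratory cells of that table are blank in the text available to me, and I draw nothing from that.

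The number of draws shows how often blood is already being taken:

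- screening: 1
- every 2 weeks for the first 2 months: about 4
- monthly for the other 10 months of year 1: about 10
- total: 1 + 4 + 10 = about 15 in the first year

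None of these draws has magnesium on its required list.

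The next step is to ask which cases this affects. Under section 3.4.3.1 an abnormal laboratory value is an adverse event only if it produces signs or symptoms, is judged clinically significant, or needs treatment. That gives three groups:

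1. **Symptomatic cases.** These can be found by history, examination or a test ordered for cause, and can be recorded under the plan as it stands.
2. **Mild, asymptomatic cases of no clinical significance.** These would not count as adverse events even if magnesium were measured.
3. **Asymptomatic cases that would be judged significant or would be treated if known.** These qualify as adverse events, but only a magnesium result reveals them, and none is scheduled.

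The gap is the third group. The documents give no incidence for hypomagnesemia, so its size cannot be estimated from them.

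**The case against.** The strongest reply is that this is a small mismatch. The lists are minimum sets, so an investigator may add magnesium, and section 3.2.5 itself gives a basis for doing so. The panel already covers sodium, potassium, chloride, bicarbonate, calcium and phosphorus, so the general instruction on electrolytes is largely met. The laboratory abnormalities that section 1.1.3.3 reports as most common, overall and at grade 3/4, include hypophosphatemia but not hypomagnesemia. Sections 3.4.5.2 and 3.4.5.4 direct grade 3-5 events to the database, which leaves out most mild cases in any event. Neither the primary endpoint nor the stopping rule in section 6.1.1 rests on magnesium.

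Most of this stands, and it limits the point without removing it. Permission to order a test does not give baseline or systematic values, and the section that calls the reaction serious is the same one that asks for monitoring.

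Three stronger readings are tempting, and the documents do not support them:

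- A reader might infer that magnesium is never measured, so that asymptomatic cases have no chance of detection. The lists show only that the test is neither scheduled nor required. A detection rate of zero would assume that no investigator ever orders it.
- A reader might infer that the reported rate will be falsely low. Because section 3.4.3.1 restricts which laboratory values are adverse events, the supportable statement is that one subset is likely to be under-ascertained.
- A reader might see a parallel gap for creatine kinase, since section 3.2.5.2 says "Patients should be monitored clinically and through serum chemistry for the development of rhabdomyolysis and other adverse events" and no muscle enzyme is listed. That sentence goes on to refer to the product labels of HMG-CoA reductase inhibitors for what is required. It names no enzyme and no frequency, so it does not contradict the lists.

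**Conclusion.** The inconsistency is real and can be confirmed by reading section 3.2.5 beside the three lists. One of four electrolyte disturbances that the protocol itself calls serious has no required test at baseline or during treatment. The consequence is confined to safety: hypomagnesemia that is asymptomatic but clinically significant is likely to be under-ascertained for the first secondary objective, by an amount the documents do not allow one to calculate. The primary analysis of 6-month progression-free survival is not affected.

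This rests on two assumptions. The first is that sites mostly run the listed tests and add magnesium only for cause. The second is that no other part of the protocol lists magnesium; a short stretch just before section 3.4.7.1 was not available to me. The point merits correction because it concerns a risk the protocol names and is cheap to close.

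**What to change.** Reconcile section 3.2.5 with sections 3.4.1.1, 3.4.1.2, 3.4.1.4 and 3.4.7.2 in one of two ways:

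- add serum magnesium to the chemistry panel already drawn at screening and on treatment, and name it in all three lists so that they agree; or
- keep the lists as they are and state in section 3.2.5 why magnesium is not monitored. The safety report should then say that hypomagnesemia was not systematically assessed.

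The first option costs one extra analyte on blood already being taken, with no added visit or needle stick. It is more than an administrative edit: section 4 gives the addition of a safety-monitoring test as an example of a change needing IRB approval, so it requires a short formal amendment. The second option costs a sentence of justification but leaves the information gap in place. Neither changes dosing, the primary endpoint or the sample size.
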